## **7.0 TRIAL PROCEDURES**

### **7.1 Trial Procedures**

The Trial Flow Chart - Section 6.0 summarizes the trial procedures to be performed at each visit. Individual trial procedures are described in detail below. It may be necessary to perform these procedures at unscheduled time points if deemed clinically necessary by the investigator.

Furthermore, additional evaluations/testing may be deemed necessary by the Sponsor and/or Merck for reasons related to subject safety. In some cases, such evaluation/testing may be potentially sensitive in nature (e.g., HIV, Hepatitis C, etc.), and thus local regulations may require that additional informed consent be obtained from the subject. In these cases, such evaluations/testing will be performed in accordance with those regulations.

#### **7.1.1 Administrative Procedures**

##### **7.1.1.1 Informed Consent**

The Investigator must obtain documented consent from each potential subject prior to participating in a clinical trial.

###### **7.1.1.1.1 General Informed Consent**

Consent must be documented by the subject's dated signature or by the subject's legally acceptable representative's dated signature on a consent form along with the dated signature of the person conducting the consent discussion.

A copy of the signed and dated consent form should be given to the subject before participation in the trial.

The initial informed consent form, any subsequent revised written informed consent form and any written information provided to the subject must receive the IRB/ERC's approval/favorable opinion in advance of use. The subject or his/her legally acceptable representative should be informed in a timely manner if new information becomes available that may be relevant to the subject's willingness to continue participation in the trial. The communication of this information will be provided and documented via a revised consent form or addendum to the original consent form that captures the subject's dated signature or by the subject's legally acceptable representative's dated signature.

Specifics about a trial and the trial population will be added to the consent form template at the protocol level.

The informed consent will adhere to IRB/ERC requirements, applicable laws and regulations and Sponsor requirements.

###### **7.1.1.2 Inclusion/Exclusion Criteria**

All inclusion and exclusion criteria will be reviewed by the investigator or qualified designee to ensure that the subject qualifies for the trial.

### **7.1.1.3 Medical History**

A medical history will be obtained by the investigator or qualified designee. Medical history will include all active conditions. Details regarding the disease for which the subject has enrolled in this study will be recorded separately and not listed as medical history.

### **7.1.1.4 Prior and Concomitant Medications Review**

#### **7.1.1.4.1 Prior Medications**

The investigator or qualified designee will review prior medication use, including any protocol-specified washout requirement, and record prior medication taken by the subject within 7 days before starting the trial. Treatment for the disease for which the subject has enrolled in this study will be recorded separately and not listed as a prior medication.

#### **7.1.1.4.2 Concomitant Medications**

The investigator or qualified designee will record medication, if any, taken by the subject during the trial. All medications related to reportable SAEs and ECIs should be recorded as defined in Section 7.2.

### **7.1.1.5 Disease Details and Treatments**

#### **7.1.1.5.1 Disease Details**

The investigator or qualified designee will obtain prior and current details regarding disease status.

#### **7.1.1.5.2 Prior Treatment Details**

The investigator or qualified designee will review all prior cancer treatments including systemic treatments, radiation and surgeries.

#### **7.1.1.5.3 Subsequent Anti-Cancer Therapy Status**

The investigator or qualified designee will review all new anti-neoplastic therapy initiated after the last dose of trial treatment. Once new anti-cancer therapy has been initiated the subject will move into survival follow-up.

### **7.1.1.6 Assignment of Screening Number**

**A screening number will be assigned to all subjected being screened.**

## **7.1.2 Clinical Procedures/Assessments**

### **7.1.2.1 Adverse Event (AE) Monitoring**

The investigator or qualified designee will assess each subject to evaluate for potential new or worsening AEs as specified in the Trial Flow Chart and more frequently if clinically indicated. Adverse experiences will be graded and recorded throughout the study treatment and during the safety follow-up period (30 days after the last dose of pembrolizumab) according to NCI CTCAE Version 4.0 (see Section 11.3). Adverse events in the post-treatment follow up period will not be recorded or reported unless they represent continuing adverse events from the treatment period related to pembrolizumab therapy.

Toxicities will be characterized in terms regarding seriousness, causality, toxicity grading, and action taken with regard to trial treatment.

For subjects receiving treatment with pembrolizumab all AEs of unknown etiology associated with pembrolizumab exposure should be evaluated to determine if it is possibly an event of clinical interest (ECI) of a potentially immunologic etiology (termed immune-related adverse events, or irAEs); see the separate ECI guidance document in Appendix 4 regarding the identification, evaluation and management of potential irAEs.

Please refer to section 7.2 for detailed information regarding the assessment and recording of AEs.

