#### **5.3.1 Acceptable Concomitant Medications**

Patients may receive hydroxyurea at the discretion of their treating hematology physician as a temporary bridge to chemotherapy. All treatments that the investigator considers necessary for a subject's welfare may be administered at the discretion of the investigator in keeping with the community standards of medical care. All concomitant medication will be recorded on the case report form (CRF) including all prescription, over-the-counter (OTC), herbal supplements, and IV medications and fluids. If changes occur during the trial period, documentation of drug dosage, frequency, route, and date may also be included on the CRF.

All concomitant medications received within 14 days before the first dose of trial treatment and 30 days after the last dose of trial treatment should be recorded. Concomitant medications administered after 30 days after the last dose of trial treatment should be recorded for SAEs and ECIs as defined in Section 7.2.

FLT-3 inhibitors and tyrosine kinase inhibitors which are resumed as part of usual care after HCT are permissible.

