Correlative Studies: Blood Collection§, ¶		X	D14 (+5)	D35 (±5)	D56 (±5)		X	D168 (±7) D252 (±7)		X	D425 (±14)†	X
Correlative Studies: Buccal Swabs		X										
Chimerism Analysis (VNTR) (Peripheral Blood)**		X		X			X			X		X

\*Phase II Maintenance treatment: For subjects achieving CR / PR as determined by day 77 response post-induction without significant pembrolizumab related toxicity. Subjects without CR / PR at day 77, relapse / progression after day 77 or clinically significant toxicity during the treatment will be considered off treatment and will be placed into follow-up.

†Follow up: Toxicity assessments will be for 30 days after last dose of pembrolizumab. Longer follow-up for up to 90 days, if applicable, based on continuing SAE / AE that was observed in the treatment period or an events of clinical interest (ECI). Follow up for survival will be up to 90 days after pembrolizumab or D455 (±14) for subjects completing

maintenance and a research blood collection will be obtained. Subjects not initiating or completing maintenance will complete 30 day toxicity assessments and then be followed only for survival (through D365 after initiating pembrolizumab). Subjects in CR/PR not completing maintenance for toxicity may have additional research specimens collected per investigators discretion (see below note). ‡ Relapse denotes collection of unplanned / unscheduled bone marrow aspirate, biopsy and correlative studies at time of clinical suspicion of relapse (if CR) or progression of malignancy at any time during treatment and follow-up periods.

§Bone marrow morphology based on aspirate and/or core biopsy, flow cytometry and  $\pm$  cytogenetics will be performed on day 35 (+5) after dose #2, day 77 ( $\pm$ 7) after dose #4, day 365 ( $\pm$ 14) after completing maintenance. An end of treatment bone marrow may be performed prior to day 365 in subjects in CR/PR who do not complete full maintenance therapy due to toxicity. Subjects removed from further treatment due to documented relapse are not required to undergo further bone marrow studies for research purposes. Cytogenetic analysis may be omitted if there are not pre-treatment cytogenetic anomalies of clinical interest.

||Comprehensive Serum Chemistry Panel should include Magnesium and Phosphorus.

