#### **7.2.3.2 Events of Clinical Interest**

Selected non-serious and serious adverse events are also known as Events of Clinical Interest (ECI) and must be reported within 24 hours to the Sponsor and within 2 working days to Merck Global Safety. (Attn: Worldwide Product Safety; [contact]).

For the time period beginning when the consent form is signed until treatment allocation/randomization, any ECI, or follow up to an ECI, that occurs to any subject must be reported within 24 hours to the Sponsor and within 2 working days to Merck Global Safety if it causes the subject to be excluded from the trial, or is the result of a protocol-specified intervention, including but not limited to washout or discontinuation of usual therapy, diet, placebo treatment or a procedure.

For the time period beginning at treatment allocation/randomization through 90 days following cessation of treatment, or 30 days following cessation of treatment if the subject initiates new anticancer therapy, whichever is earlier, any ECI, or follow up to an ECI, whether or not related to Merck product, must be reported within 24 hours to the Sponsor and within 24 hours to Merck Global Safety.

Events of clinical interest for this trial include:

1. an overdose of Merck product, as defined in Section 7.2.1 - Definition of an Overdose for This Protocol and Reporting of Overdose to the Sponsor, that is not associated with clinical symptoms or abnormal laboratory results.
2. When **NOT** deemed to be related to underlying leukemia, an elevated AST or ALT lab value that is **greater than or equal to 5X** the upper limit of normal and an elevated total bilirubin lab value that is greater than or equal to 2X the upper limit of normal and, at the same time, an alkaline phosphatase lab value that is less than 2X the upper limit of normal, as determined by way of protocol-specified laboratory testing or unscheduled laboratory testing.\*

**\*Note:** These criteria are based upon available regulatory guidance documents. The purpose of the criteria is to specify a threshold of abnormal hepatic tests that may require an additional evaluation for an underlying etiology.

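### Sections 7.1.2.1 and 7.2.3.2 define events of clinical interest differently, so late non-serious immune events and the 90-day GvHD count in 8.2.1 have no settled collection rule

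*Combined protocol and SAP*

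**What the plan says.** Section 7.1.2.1 does two things. It tells the investigator to assess adverse events of unknown cause in exposed subjects as "possibly an event of clinical interest (ECI) of a potentially immunologic etiology (termed immune-related adverse events, or irAEs", which makes an immune-related event a kind of ECI. It also sets the recording period. Events are recorded on treatment and "during the safety follow-up period (30 days after the last dose of pembrolizumab"; after that, "Adverse events in the post-treatment follow up period will not be recorded or reported unless they represent continuing adverse events from the treatment period" and are related to the drug. For immune-related events it adds a pointer: "see the separate ECI guidance document in Appendix 4".

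Section 7.2.3.2 gives the ECI reporting duty. Any ECI, related or not, goes to the sponsor within 24 hours, through 90 days after treatment stops, or 30 days if new anticancer therapy starts first. Under the words "Events of clinical interest for this trial include" it lists two items. The first is "an overdose of Merck product, as defined in Section 7.2.1", without symptoms or abnormal laboratory results. The second is raised AST or ALT with raised bilirubin and alkaline phosphatase below twice the upper limit. Neither immune-related events nor GvHD appear.

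Two other rules depend on ECI status. The footnote to the Section 6.0 flow chart allows toxicity follow-up to 90 days "based on continuing SAE / AE that was observed in the treatment period or an events of clinical interest (ECI". Section 5.3.1 says that medications given more than 30 days after the last dose "should be recorded for SAEs and ECIs as defined in Section 7.2".

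On the analysis side, 4.2.2.1 and 8.2.1 list the incidence of immune-mediated toxicity as a safety endpoint, with no grade or time window on that line. Section 8.2.1(b) counts acute GvHD of grade 2-4 and new chronic GvHD through 90 days after the last infusion.

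**The concern.** A collection rule that turns on a term needs one definition of that term, and here there are two. They disagree on the class of event the trial most needs to count. Section 5.2.1.2 itself expects drug-associated events to appear several weeks after the last dose, so late onset is foreseen.

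If a site follows the list in 7.2.3.2, a new low-grade colitis or endocrine event at, say, day 50 after the last dose is an ordinary adverse event and is not recorded. If it follows 7.1.2.1, the same event is an ECI and is reported. The recording of any steroid course given for it follows the same split through 5.3.1. An event that was never recorded may not be recoverable later, and an incidence built from such data would partly reflect how sites read the protocol.

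GvHD raises a related problem. The analysis plans a 90-day count, while the recording rules, read literally, stop at 30 days for new non-serious events.

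**Working it through.** The plan states no figure on this point, so the check is a comparison of the rules.

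**Interval in dispute.** General recording ends 30 days after the last dose (7.1.2.1; 7.2 and 7.1.4.3 use the same 30 days). The ECI duty ends at 90 days after treatment stops (7.2.3.2), taken here as 90 days after the last dose. The interval is days 31 to 90, that is 90 − 30 = 60 days, for subjects who have not started new anticancer therapy. For those who have, both windows close at 30 days.

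**A new, non-serious immune event in that interval.**
- Reading A: 7.1.2.1 governs what an ECI is. The event is an ECI, the 90-day rule in 7.2.3.2 applies, the flow-chart footnote extends toxicity follow-up, and 5.3.1 requires the related medications to be recorded.
- Reading B: the list in 7.2.3.2 governs. The event is not an ECI. The bar in 7.1.2.1 on new follow-up events applies, and neither the event nor its treatment is recorded.

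The split is thus between two definitions. Section 7.1.2.1 supplies both the classification that would keep the event and the sentence that would drop it; the 90-day duty sits in 7.2.3.2.

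**Events that come out the same on either reading.**
- Serious events judged related to the drug: 7.2.3.1 makes them reportable at any time.
- Immune hepatitis meeting the liver-test pattern: it is on the list.
- Events continuing from the treatment period and related to the drug: 7.1.2.1 keeps them.
- Events on treatment and to 30 days: captured either way. Only the speed of reporting differs.

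**GvHD.**
- Section 8.2.1(b) counts to 90 days after the last infusion, across induction and maintenance.
- Section 7.2 requires reporting of non-hematologic events of grade 3 or higher, to 30 days.
- Section 7.1.2.1 bars new events after that, and 7.2.3.2 does not list GvHD.
- The flow-chart footnote moves subjects who do not start or complete maintenance to survival-only follow-up after the 30-day toxicity assessment.

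No recording rule therefore clearly requires new non-serious grade 2 or higher acute GvHD, or new chronic GvHD, to be collected on days 31 to 90, although the analysis counts it.

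**Which analyses are touched.**
- Immune-toxicity incidence (4.2.2.1, 8.2.1): yes, because the line has no window.
- GvHD count in 8.2.1(b): yes.
- Grade 3 or higher immune toxicity in 8.1: not materially, since it is estimated at 30 days after the last dose.
- Interim halts in 8.2.4 (6 of 10, 9 of 15): not materially, since they count severe acute GvHD, observed for 30 days after the last induction dose.

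**Size.** With 20 subjects, each missed subject would move an incidence by 1/20 = 5 percentage points. The number missed cannot be derived, because the documents give no rate of late non-serious immune events and no expected number of subjects with an open day 31-90 window.

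**The case against.** The best defence is that the list need not be exhaustive. Its opening, "Events of clinical interest for this trial include", leaves room for more, and 7.1.2.1 sends the reader to a guidance document in an Appendix 4. That document is not among the supplied appendices (11.1 to 11.3), and nothing should be inferred from its absence, since it is described as separate. The defence does not settle the matter. Section 7.1.2.1 describes the guidance as covering how immune events are identified, evaluated and managed, not how long they are reported. Section 5.3.1 points for its definition to Section 7.2, where the list stands. A 24-hour duty should not rest on inference.

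It is also fair that the flow chart marks adverse-event review in the column for the 30- and 90-day follow-up. That schedules a review; 7.1.2.1 still governs what is recorded from it. Likewise, 8.2.1(b) states what will be counted for GvHD, but an analysis definition does not create a collection rule.

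Two stronger readings are tempting and do not hold.

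- A reader might infer that safety stopping is compromised. The interim halts do not use these events. In the 12-of-20 criterion, GvHD is monitored to 30 days after the last induction dose. Its immune-event part has no stated window, but it requires grade 3 or higher events that fail to improve to grade 1 after 14 days of systemic corticosteroids. Few of those are likely to stay non-serious, and related serious events are always reportable.
- A reader might assume that 10-20% of 20 subjects, that is 2 to 4, have such an event, and quote a 10-20 point difference in incidence. That rate has no source in the documents. It also ignores that the ECI window closes at 30 days once new anticancer therapy starts, and that only subjects in CR or PR at day 77 may enter maintenance.

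**Conclusion.** The contradiction stands, within limits. For new, non-serious immune-related events 31 to 90 days after the last dose, in subjects without new anticancer therapy, the protocol supports both capture and omission. For GvHD, the recording rules fall short of the 90-day count that 8.2.1(b) plans. The quantities at risk are that count and the unwindowed immune-toxicity incidence; both would tend to be under-collected.

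The size cannot be stated beyond the 60-day interval, and no 10-20 point effect can be supported. The conclusion assumes that no unseen guidance document sets a different reporting window. The passages should be reconciled before the 90-day data are relied on.

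**What to change.** 1. In 7.2.3.2, keep one ECI definition and state there that adverse events judged immune-related under 7.1.2.1 are ECIs.
2. In 7.1.2.1, add an exception to the 30-day bar: new immune-related events, new acute GvHD of grade 2-4 and new chronic GvHD are recorded through 90 days after the last dose.
3. Align the flow-chart footnote, including its survival-only follow-up for subjects not starting or completing maintenance, and the medication rule in 5.3.1 with that exception.

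GvHD needs recording to 90 days to support 8.2.1(b), but need not become a 24-hour report. Section 8.2.4 treats it as distinct from immune toxicity and expects grade 2-4 acute GvHD in 40-50% of subjects even without the drug, so expediting every case would add workload without improving the count.

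The cost is a wording amendment, some extra recording between days 31 and 90, and some additional expedited immune-event reports. The reported late-toxicity rate may rise slightly because more events are captured.

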#### **7.1.2.2 Full Physical Exam**

The investigator or qualified designee will perform a complete physical exam during the screening period. Clinically significant abnormal findings should be recorded as medical history. A full physical exam should be performed during screening.

#### **7.1.2.3 Directed Physical Exam**

For cycles that do not require a full physical exam per the Trial Flow Chart, the investigator or qualified designee will perform a directed physical exam as clinically indicated prior to trial treatment administration.

#### **7.1.2.4 Vital Signs**

The investigator or qualified designee will take vital signs at screening, prior to the administration of each dose of trial treatment and at treatment discontinuation as specified in the Trial Flow Chart (Section 6.0). Vital signs should include temperature, pulse, respiratory rate, weight and blood pressure. Height will be measured at screening only.

#### **7.1.2.5 Eastern Cooperative Oncology Group (ECOG) Performance Scale**

The investigator or qualified designee will assess ECOG status (see Section 11.1) at screening, prior to the administration of each dose of trial treatment and discontinuation of trial treatment as specified in the Trial Flow Chart. As Karnofsky performance score is commonplace in BMT clinical practice and research, this scale is acceptable in place of ECOG (Appendix 11.2)

#### **7.1.2.6 Tumor Tissue Collection and Correlative Studies Blood Sampling**

See section 7.1.3.1.3

### **7.1.3 Laboratory Procedures/Assessments**

Details regarding specific laboratory procedures/assessments to be performed in this trial are provided below. Laboratory Safety Evaluations (Hematology, Chemistry and Urinalysis)

Laboratory tests for hematology, chemistry, urinalysis, and others are specified in Table 5.

**Table 5 Laboratory Tests**

Hematology	Chemistry	Urinalysis	Other
Hematocrit	Albumin	Blood	Serum $\beta$ -human chorionic gonadotropin†
Hemoglobin	Alkaline phosphatase	Glucose	( $\beta$ -hCG)†
Platelet count	Alanine aminotransferase (ALT)	Protein	PT (INR)
WBC (total and differential)	Aspartate aminotransferase (AST)	Specific gravity	aPTT
Red Blood Cell Count	Lactate dehydrogenase (LDH)	Microscopic exam ( If abnormal )	Total triiodothyronine (T3)
Absolute Neutrophil Count	Carbon Dioxide ‡	results are noted	Free tyroxine (T4)
Absolute Lymphocyte Count	( $CO_2$ or bicarbonate)	Urine pregnancy test †	Thyroid stimulating hormone (TSH)
	Uric Acid		PK
	Calcium		
	Chloride		Blood for correlative studies
	Glucose		
	Phosphorus		
	Potassium		
	Sodium		
	Magnesium		
	Total Bilirubin		
	Direct Bilirubin ( If total bilirubin is elevated above the upper limit of normal )		
	Total protein		
	Blood Urea Nitrogen		

† Perform on women of childbearing potential only. If urine pregnancy results cannot be confirmed as negative, a serum pregnancy test will be required.

‡ If considered standard of care in your region.

### **7.1.3.1 Pharmacokinetic/Pharmacodynamic and Laboratory correlation Evaluations**

#### **7.1.3.1.1 Blood Collection for Serum pembrolizumab**

Sample collection, storage and shipment instructions for serum samples will be provided in the Laboratory Manual.

The time points for PK blood sampling are described in Section 6 – Trial Flow Chart.

